9.7. Disclosure

A description of this clinical study will be available on <http://www.ClinicalTrials.gov>, as well as other country-specific registries, as required by US law and/or other country laws.

9.8. Biological Specimens and Data

Blood and bone marrow specimens will be cryopreserved and biobanked for additional analyses. These samples will be retained for long-term storage by the Sponsor and described in the informed consent.

Any blood, tissue, or biomarker sample collected according to the Schedule of Assessments (Section 4.3) may be analyzed prior to or after study unblinding for any tests outlined in the protocol. This includes testing to ensure that analytical methods produce reliable and valid data throughout the course of the study. It may also include, but is not limited to, investigation of unexpected results, incurred sample reanalysis, and analyses for method transfer comparability.

All samples and associated results will be coded prior to being shipped from the site for analysis or storage. Samples will be tracked using a unique identifier that is assigned to the samples for the study. Results are stored in a secure database to ensure data integrity and control. Samples may be retained for up to 15 years.

If permitted by local law and if informed consent is provided by the participant, Gilead Sciences, Inc. may do additional testing on remaining samples (i.e., residual and back-up) to investigate and better understand MDS and the dose response and/or prediction of response to magrolimab, to characterize antibody response, and to characterize aspects of the molecule (e.g., MOA/target, metabolites). Results from this analysis are to be documented and maintained but are not necessarily reported as part of this study.

Since the evaluations are not expected to benefit the participant directly or to alter the participant's treatment course, the results of these exploratory studies are not placed in the participant's medical record and are not to be made available to the participant, members of the participant's family, the participant's personal physician, or other third parties, except as specified in the ICF.

The participant retains the right to request that the sample material be destroyed by contacting the Investigator. Following the request from the participant, the Investigator is to provide the Sponsor with the required study and patient number so that any remaining blood samples and any other components from the cells can be located and destroyed. Samples will be destroyed once all protocol-defined procedures have been completed.

Information collected from samples prior to the request for destruction will be retained by the Sponsor. The Sponsor is the exclusive owner of any data, discoveries, and derivative materials from the sample materials and is responsible for the destruction of the sample(s) at the request of the participant through the Investigator, at the end of the storage period or as appropriate (e.g., the scientific rationale for experimentation with a certain sample type no longer justifies keeping the sample). If a commercial product is developed from this research project, the Sponsor owns the commercial product. The participant has no commercial rights to such product and has no commercial rights to the data, information, discoveries, or derivative materials gained or produced from the sample.

9.8.1. Payment Reporting

Investigators and their study staff may be asked to provide services performed under this protocol (e.g., attendance at Investigator meetings). If required under the applicable statutory and regulatory requirements, Gilead will capture and disclose to federal and state agencies any expenses paid or reimbursed for such services, including any clinical study payments, meal, travel expenses or reimbursements, consulting fees, and any other transfer of value.

10. OVERSIGHT

10.1. Independent Monitoring

10.1.1. DMC

The DMC will review the unblinded data generated during the clinical study. The mandate of the DMC is to serve as an independent committee with pertinent clinical and study conduct expertise to monitor and ensure the safety of the therapies for participants on study. The composition, structure, and function of the DMC and the scope of data for review are defined in the DMC Charter. The timing of such data review will be predefined in the DMC Charter.

10.2. Quality Control and Assurance

10.2.1. Monitoring

The Gilead Sciences, Inc. representative(s) are responsible for contacting and visiting the Investigator for the purpose of inspecting the facilities and, upon request, inspecting the various records of the clinical study (e.g., eCRFs and other pertinent data) provided that participant confidentiality is respected.

The Gilead Sciences, Inc. representative(s) are responsible for verifying the eCRFs at regular intervals throughout the study to verify adherence to the protocol; completeness, accuracy, and consistency of the data; and adherence to local regulations on the conduct of clinical research. The Gilead Sciences, Inc. representative(s) are to have access to participant medical records and other study-related records needed to verify the entries on the eCRFs.

The Investigator agrees to cooperate with the Gilead Sciences, Inc. representative(s) to ensure that any problems detected in the course of these monitoring visits, including delays in completing eCRFs, are resolved.

10.2.2. Audits

As stipulated by 21 CFR §312.58 and ICH guidelines for GCP, a representative of the Sponsor or regulatory agency may conduct periodic site audits or inspections. The Investigator or designee will provide these representatives with access to all requested materials, including eCRFs and supporting source documents. In addition, the Investigator or other qualified study site personnel are to be available to answer questions, hold interviews, and provide facility tours if requested.

10.2.3. Records

10.2.3.1. Data Capture and Management

The Investigator is responsible for complying with the requirements for all assessments and data collection (including participants not receiving protocol-required therapies), as stipulated in the protocol for each participant in the study. For participants who discontinue from the study prior

to completion of all protocol-required visits for study assessments or survival follow-up as described in Section 4.3, the Investigator may search publicly available records (where permitted by local laws and regulations) to ascertain survival status. This ensures reduced risk of missing critical efficacy data.

The Investigator agrees to maintain adequate case histories for the participants treated as part of the research under this protocol. Data collection will involve the use of the EDC system, to which only authorized personnel will have access. The Investigator agrees to maintain accurate eCRFs and source documentation as part of the case histories.

The Investigator or designee must enter all results collected during the clinical study into eCRFs. Guidelines for completion of eCRFs will be reviewed with study site personnel at the site initiation visits. Investigators are responsible for approval of the entered/corrected data. At a minimum, prior to any interim time points or database lock (as instructed by Gilead), the Investigator will use his/her log-in credentials to confirm that the forms have been reviewed, and that the entries accurately reflect the information in the source documents. Detailed instructions are provided in the other study-specific documents.

All entries made on the eCRF may require verification against source documents. In addition to periodic monitoring occurring within the system by study monitors, programmatic edit checks and data listings will be used to review the data for completeness, logic, and adherence to study protocol. As a result of this monitoring and these checks, queries may be electronically issued to the clinical study sites and electronically resolved by those sites.

All data collected in the context of this study will be stored and evaluated according to regulatory requirements and applicable guidance for electronic records. Also, data will be stored and evaluated in such a way as to assure participant confidentiality in accordance with the legal and regulatory requirements applying to protected health information. Study records (e.g., copies of eCRFs, regulatory documents) will be retained at the study site, along with adequate source documentation. The study file and all source data must be retained for the time period required by applicable regulatory requirements and will not be destroyed until written notification is given by the Sponsor or designee for destruction.

10.2.3.2. Source Documentation

As stipulated by 21 CFR §312.57 and ICH E6 GCP Consolidated Guidance Section 8, the Investigator or designee will maintain source documentation for this clinical study that documents the treatment and study course of participants.

The source data for this study may be obtained from EDC and central or local laboratory reports. Source documents are original documents, data, and records from which the participant's eCRF data are obtained. These include, but are not limited to, hospital records, clinical and office charts, laboratory and pharmacy records, diaries, microfiches, radiographs, and correspondence.

10.2.3.3. Study Files

The Investigator and study staff are responsible for maintaining a comprehensive and centralized filing system of all study-related (essential) documentation, suitable for inspection at any time by representatives from Gilead Sciences, Inc. and/or applicable regulatory authorities.

10.2.3.4. Records Retention

The Investigator must retain all essential documents for this clinical study until at least 2 years after the last approval of a marketing application in an ICH region and until there are no pending or contemplated marketing applications in an ICH region, or until at least 2 years have elapsed since the formal discontinuation of clinical development of magrolimab. However, the Investigator may need to retain these documents for a longer period, if required by the applicable regulatory requirements or by an agreement with the Sponsor. A Sponsor representative will be responsible for informing the Investigator and study site regarding when they no longer need to retain these documents. Before destroying any records, the Investigator must notify the Sponsor and reach agreement on record destruction, or the Sponsor may request an additional retention period.

10.3. Serious Breaches or Fraud

A serious breach is defined as “A breach of GCP or the study protocol which is likely to effect to a significant degree:

- the safety or physical or mental integrity of the participants of the study; or
- the scientific value of the study”

Investigators or designee must notify Gilead Sciences, Inc. immediately if any serious breach of GCP is suspected and prior to notifying IRB/IECs.

If there is any proof of fraud, this must also be reported to Gilead Sciences, Inc. If any additional local or national reporting is required, this must also be done.

10.4. Study Termination or Study Site Closure

Gilead Sciences, Inc. reserves the right to terminate the study at any time. Both Gilead Sciences, Inc. and the Investigator reserve the right to terminate the Investigator’s participation in the study according to the study contract. The Investigator is to notify the IRB/IEC in writing of the study’s completion or early termination and send a copy of the notification to Gilead Sciences, Inc.

The study may also be terminated for safety reasons.

11. FINANCIAL DISCLOSURE AND INSURANCE

The Sponsor maintains clinical study insurance coverage for this study in accordance with the laws and regulations of the country in which the study is performed.

The Investigator and Subinvestigators will provide prompt and accurate documentation of their financial interest or arrangements with Gilead or proprietary interests in the study drug during the course of a clinical study. This documentation must be provided prior to the Investigator's (and any Subinvestigator's) participation in the study. The Investigator and Subinvestigator agree to notify Gilead of any change in reportable interests during the study and for 1 year following completion of the study. Study completion is defined as the date when the last participant completes the protocol-defined activities.

13. APPENDICES

Appendix A. National Cancer Institute Common Terminology Criteria for Adverse Events

Common Terminology Criteria for Adverse Events (CTCAE) of the National Cancer Institute (NCI), Version 5.0

Publication date: 27 November 2017 (v5.0)

https://ctep.cancer.gov/protocoldevelopment/electronic_applications/docs/CTCAE_v5_Quick_Reference_8.5x11.pdf

Accessed 18 February 2020

Appendix B. Disease Response Assessment Based on International Working Group Criteria

Response will be assessed in myelodysplastic syndrome (MDS) patients using the 2006 International Working Group (IWG) criteria {Cheson 2006} as shown in Table 19. In addition, complete remission (CR) with partial hematologic recovery (CRh) will be assessed for MDS, defined as patients who achieve a CR per IWG 2006 MDS criteria {Cheson 2006}, with the exception of requiring partial hematologic recovery as defined by a platelet count of $> 50 \times 10^9/L$ and an absolute neutrophil count of $> 500/\mu L$.

In addition, HI will be assessed by 2006 IWG criteria {Cheson 2006} (Table 21) and cytogenetic/molecular response by 2003 IWG criteria {Cheson 2003} (Table 20).

Table 19. Response Criteria in MDS (IWG 2006 Criteria With Modifications)

Category	Response Criteria
CR	Bone marrow $\leq 5\%$ myeloblasts with normal maturation of all cell lines ^a Persistent dysplasia will be noted ^{a,b} Peripheral blood ^c Hgb ≥ 11 g/dL Platelets $\geq 100 \times 10^9/L$ Neutrophils $\geq 1.0 \times 10^9/L^b$ Blasts 0%
PR	All CR criteria if abnormal before treatment except: Bone marrow blasts decreased by $\geq 50\%$ over pretreatment but still $> 5\%$ Cellularity and morphology not relevant
Marrow CR ^b	Bone marrow $\leq 5\%$ myeloblasts and decrease by $\geq 50\%$ over pretreatment ^b Peripheral blood: if HI responses, they will be noted in addition to marrow CR ^b
Stable Disease	Failure to achieve at least PR, but no evidence of progression for > 8 weeks
Failure	Death during treatment or disease progression characterized by worsening cytopenias, increase in percentage of bone marrow blasts, or progression to a more advanced MDS FAB subtype than pretreatment
Relapse after CR or PR	At least 1 of the following: Return to pretreatment bone marrow blast percentage Decrement of $\geq 50\%$ from maximum remission/response levels in granulocytes or platelets Reduction in Hgb concentration by ≥ 1.5 g/dL or transfusion dependence ^d
Cytogenetic Response	Complete: Disappearance of chromosomal abnormality without appearance of new ones Partial: At least 50% reduction of the chromosomal abnormality
Disease Progression	For patients with: Less than 5% blasts: ≥ 50 increase in blasts to $> 5\%$ blasts 5%-10% blasts: $\geq 50\%$ increase in blasts to $> 10\%$ blasts 10%-20% blasts: $\geq 50\%$ increase in blasts to $> 20\%$ blasts 20%-30% blasts: $\geq 50\%$ increase in blasts to $> 30\%$ blasts Any of the following: At least 50% decrement from maximum remission/response in granulocytes or platelets Reduction in Hgb by ≥ 2 g/dL ^d Transfusion dependence ^d

Source: {Cheson 2006}

Abbreviations: CR = complete remission; FAB = French-American-British classification; Hgb = hemoglobin; HI = hematologic improvement; IWG = International Working Group; MDS = myelodysplastic syndrome; PR = partial remission.

- a Dysplastic changes should consider the normal range of dysplastic changes.
- b Modification to IWG response criteria.
- c Transient cytopenias during repeated chemotherapy courses should not be considered as interrupting durability of response, as long as they recover to the improved counts of the previous course.
- d Impact of anemia must be deemed disease-related and not due to study treatment.

Table 20. Additional Response Definitions Used in This Study (2003 IWG Criteria)

Response Criteria	Definitions			
	Neutrophils	Platelets	Bone Marrow Blasts	Other
cCR	$\geq 1.0 \times 10^9/L$	$\geq 100 \times 10^9/L$	< 5%	Cytogenetics normal and no evidence of extramedullary disease
mCR	$\geq 1.0 \times 10^9/L$	$\geq 100 \times 10^9/L$	< 5%	Molecular investigations normal and no evidence of extramedullary disease
Treatment Failure ^a	Lack of response/Progressive Disease + loss of clinical benefit			

Source: {Cheson 2003}

Abbreviations: cCR = cytogenetic complete remission; IWG = International Working Group; mCR = molecular complete remission.

a Treatment failure defined for this protocol

Table 21. Response Criteria for Hematologic Improvement

Hematologic Improvement (HI) Category ^a	Response Criteria (all responses must last ≥ 8 weeks)
Erythroid Response (HI-E) (pretreatment < 110 g/L)	Pretransfusion increase in hemoglobin by 15 g/L or Compared to an 8-week pretreatment period, a reduction in transfusion requirements by 4 units in an 8-week posttreatment period
Platelet Response (HI-P) (pretreatment < $100 \times 10^9/L$)	Absolute increase of $\geq 30 \times 10^9/L$ for patient starting with a platelet count $> 20 \times 10^9/L$ pretreatment or Increase from $< 20 \times 10^9/L$ pretreatment to $> 20 \times 10^9/L$ posttreatment and by at least 100%
Neutrophil Response (HI-N) (pretreatment < $1.0 \times 10^9/L$)	At least 100% increase and an absolute increase of $> 0.5 \times 10^9/L$
Progression/relapse after Hematological Improvement ^b	One or more of the following $\geq 50\%$ decrement from maximum response in neutrophils or platelets Reduction in hemoglobin by ≥ 15 g/L Transfusion dependence

Source: {Cheson 2006}

a Pretreatment counts should be an average of at least 2 measurements (not influenced by transfusions) performed ≥ 1 week apart.

b In the absence of another explanation. For example, including, but not restricted to, acute infection, gastrointestinal bleeding and hemolysis.

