1. SYNOPSIS

Title	A Randomized, Double-blind, Multicenter Study Comparing Magrolimab in Combination with Azacitidine versus Azacitidine Plus Placebo in Treatment-naïve Patients with Higher Risk Myelodysplastic Syndrome
Short Title	Magrolimab + Azacitidine versus Azacitidine + Placebo in Untreated MDS
Acronym	ENHANCE: Efficacy of a Novel Hu5F9-G4 + Azacitidine Therapy in Treatment-Naïve Patients with Myelodysplastic Syndrome
Phase	3
Study Design	This is a randomized, double-blind, placebo-controlled, multicenter study investigating magrolimab + azacitidine compared with azacitidine + placebo in previously untreated participants with intermediate/high/very high risk myelodysplastic syndrome (MDS) by Revised International Prognostic Scoring System (IPSS-R).
Rationale	Novel therapies that can be combined with hypomethylating agents while maintaining an acceptable safety profile and improving durable complete remissions or survival probability are needed for individuals with higher risk MDS. No new therapies have been approved in MDS for over a decade, which underscores a high unmet medical need in this population. Patients with MDS experience frequent comorbidities and mortalities as a result of cytopenias due to the disease and to hypomethylating agents. The need for combination therapies that can induce hematologic improvement and disease remission leading to a clear clinical benefit is quite evident. Magrolimab in combination with azacitidine is being developed in previously untreated participants with intermediate/high/very high risk MDS by IPSS-R to improve clinical activity and maintain an acceptable safety profile.
Target Population	Previously untreated participants \geq 18 years of age with MDS defined according to World Health Organization classification with an IPSS-R risk category of intermediate, high, or very high risk.
Number of Participants	Total: Approximately 520 participants globally

Length of Participation	
On treatment: Until disease progression, loss of clinical benefit, or unacceptable toxicities occur
 
On study (including screening and follow-up): Up to 4 years after the last participant is randomized
						

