Abbreviations: CBC = complete blood count; EQ-5D-5L = 5-level EuroQol 5 dimensions; FACT-Anemia = Functional Assessment of Cancer Therapy-Anemia; MRD = minimal residual disease; PGIC = Patient Global Impression of Change; PGIS = Patient Global Impression of Severity; PRO = patient-reported outcome; Q2C = every 2 cycles; Q3C = every 3 cycles.

- a Four PRO questionnaires will be administered in this study: the FACT-Anemia questionnaire, the EQ-5D-5L, the PGIS, and the PGIC. The participant should complete these questionnaires before other study procedures at required visits. No PGIC assessment at Cycle 1 Day 1. FACT-Anemia and EQ-5D-5L should be implemented prior to PGIS/PGIC.
- b If magrolimab and azacitidine are administered on the same day, only one such study assessment is needed. Assessments should be performed prior to study treatment administration. Pretreatment assessments for the initial dose (Cycle 1 Day 1) may be collected up to 72 hours before administration of study treatment; thereafter, pretreatment assessments are to be collected within 24 hours prior to study treatment administration.
- c Bone marrow biopsy samples will be collected at Day 1 of Cycles 3 and 10.
- d An aspirate sample will be collected for response assessment, biomarker studies, and MRD assessment. Conventional cytogenetics to be tested per institutional standards. Response assessments may be adjusted by ± 1 week for Cycle 3 Day 1. After Cycle 3 Day 1, the window is ± 14 days.
- e An aspirate sample will be collected for biomarker studies at Day 1 of Cycles 3, 5, 7, 10, and 13.
- f Samples will be collected at Day 1 of Cycles 3, 5, and 7 and then every 3 cycles thereafter during study treatment. Bone marrow aspirate biopsies for response assessments may be adjusted by ± 1 week for Cycle 3 Day 1. After Cycle 3 Day 1, the window is ± 14 days.
- g Vital signs will be assessed prior to infusion/injection of each study treatment. Weight will be assessed on Day 1 of each cycle. Details are provided in Section 5.1.5.
- h If azacitidine and magrolimab/placebo are administered on the same day, azacitidine administration should be completed at least 1 hour before magrolimab/placebo administration. Azacitidine may be administered on an alternative schedule of Days 1 to 5, Day 8, and Day 9 of a 28-day cycle for flexibility and convenience.

Table 4. Schedule of Assessments - Treatment Period-Magrolimab or Placebo Dosing and Study Assessments

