8.4. Endpoint Definitions

Response will be assessed using the criteria in [Appendix B, Table 19](#), which are based on the 2006 IWG criteria {[Cheson 2006](#)}. In addition, hematologic improvement (HI) will be assessed by 2006 IWG criteria {[Cheson 2006](#)} and cytogenetic/molecular response by 2003 IWG criteria {[Cheson 2003](#)}.

Response assessments will be performed at the time points specified in the Schedule of Assessments in [Section 4.3](#) and as described in [Section 5.3](#).

The following summary measures for endpoints will be evaluated:

CR Rate: The CR rate is the proportion of participants who reach morphologic CR (morphological blast of $\leq 5\%$ and recovery of ANC, platelets, and hemoglobin from CBCs as well as peripheral blast collected on the same day) based on Investigator-assessed IWG 2006 MDS criteria {Cheson 2006} prior to initiation of any new anticancer therapy, including SCT.

Duration of CR: The duration of CR is measured from the time measurement criteria are first met for CR to the first date of relapse or death, whichever occurs earlier. Those who are not observed to relapse or die will be censored at their last response assessment date with evidence of no relapse. Participants who achieve a CR and then proceed to an allogeneic SCT will continue to be followed for the response assessment posttransplant, will be included in the analysis of duration of CR, and will not be censored at the time of transplant.

Overall Survival (OS): The length of OS is measured from randomization to the date of death from any cause. Those who are not observed to die during the study will be censored at their last known alive date.

Objective Response Rate (ORR): The ORR is the proportion of participants who reach objective response including CR, PR, marrow CR, or hematologic improvement per IWG 2006 MDS criteria prior to initiation of any new anticancer therapy, including SCT.

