Duration of Response (DOR): The DOR is measured from the time measurement criteria are first met for objective response to the first date of relapse, disease progression or death, whichever occurs earlier. Those who are not observed to relapse, disease progress or die will be censored at their last response assessment date with evidence of no relapse/no disease progression. Participants who achieve a response and then proceed to an allogeneic SCT will continue to be followed for the DOR posttransplant, will be included in the analysis of DOR, and will not be censored at the time of transplant.

RBC Transfusion Independence Rate: The RBC transfusion independence rate is the proportion of participants who have a 56-day or longer period with no RBC transfusions at any time between randomization and initiation of any new anticancer therapy, including SCT, among all participants who are RBC transfusion-dependent at baseline.

Progression-free Survival (PFS): The length of PFS is defined as the time from randomization to the date of documented disease progression (including treatment failure by IWG criteria or relapse after PR/CR), or death from any cause, whichever occurs first. Those who are not observed to have one of these events will be censored at their last response assessment date with evidence of no disease progression/relapse.

Event-free Survival (EFS): The length of EFS is defined as the time from randomization to transformation to AML or death from any cause, whichever occurs first. Participants who are not observed to have one of these events during the study will be censored at their last response assessment date with evidence of no transformation to AML.

MRD-negative Response Rate: The MRD-negative response rate is defined as the proportion of participants who achieve a morphologic CR or marrow CR based on Investigator-assessed IWG criteria {Cheson 2006} and reach MRD-negative disease status prior to initiation of any new anticancer therapy, including SCT. MRD-negative disease status will be assessed using a multiparameter flow cytometry-based assay performed by a central laboratory.

Time to Transformation to AML: Time to transformation to AML is defined as the time from randomization to the collection date of bone marrow sample leading to documented AML diagnosis. Participants who are not observed to have transformation to AML will be censored at their last response assessment date with evidence of no AML diagnosis.

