Appendix 2. Disease Response Assessment Based on International Working Group Criteria

Response will be assessed in myelodysplastic syndrome (MDS) patients using the 2006 International Working Group (IWG) criteria {Cheson 2006} with modifications as shown in Appendix Table 6. In addition, complete remission (CR) with partial hematologic recovery (CRh) will be assessed for MDS, defined as patients who achieve a CR per IWG 2006 MDS criteria {Cheson 2006}, with the exception of requiring partial hematologic recovery as defined by a platelet count of $> 50 \times 10^9$ /L and an absolute neutrophil count of $> 500/\mu$ L.

In addition, HI will be assessed by 2006 IWG criteria {Cheson 2006}; Appendix Table 8) and cytogenetic/molecular response by 2003 IWG criteria {Cheson 2003}; Appendix Table 7).

Category	Response Criteria
CR	Bone marrow \leq 5% myeloblasts with normal maturation of all cell lines ^a
	Persistent dysplasia will be noted ^{a,b}
	Peripheral blood ^c
	$Hgb \ge 11 g/dL$
	Platelets $\geq 100 \times 10^9/L$
	Neutrophils $\geq 1.0 \times 10^9/L^b$
	Blasts 0%
PR	All CR criteria if abnormal before treatment except:
	Bone marrow blasts decreased by $\geq 50\%$ over pretreatment but still $> 5\%$
	Cellularity and morphology not relevant
Marrow CR ^b	Bone marrow \leq 5% myeloblasts and decrease by \geq 50% over pretreatment ^b
	Peripheral blood: if HI responses, they will be noted in addition to marrow CR ^b
Stable Disease	Failure to achieve at least PR, but no evidence of progression for > 8 weeks
Failure	Death during treatment or disease progression characterized by worsening cytopenias, increase in percentage of bone marrow blasts, or progression to a more advanced MDS FAB subtype than pretreatment
Relapse after CR	At least 1 of the following:
or PR	Return to pretreatment bone marrow blast percentage
	Decrement of \geq 50% from maximum remission/response levels in granulocytes or platelets
	Reduction in Hgb concentration by ≥ 1.5 g/dL or transfusion dependence ^d
Cytogenetic	Complete: Disappearance of chromosomal abnormality without appearance of new ones
Response	Partial: At least 50% reduction of the chromosomal abnormality

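### Marrow CR, which alone makes an ORR responder, has no baseline-blast requirement, so a chance halving of an already low blast count (for example 2% to 1%) can score as a response

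*Protocol*

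**What the plan says.** - **Criterion.** Protocol Appendix B, Table 19 defines marrow CR as at most 5% marrow "myeloblasts and decrease by $\geq 50\%$ over pretreatment". SAP Appendix 2, Appendix Table 6 repeats the row ("myeloblasts and decrease by" at least 50%). Both tables footnote it as a modification of the IWG criteria, so the wording is the sponsor's own. Any haematologic improvement (HI) is noted but not required.
- **Use.** Protocol 8.4 defines ORR by "objective response including CR, PR, marrow CR, or hematologic improvement per IWG 2006 MDS criteria"; SAP 6.2.1 uses the same list. DOR starts when objective response is first met. The MRD-negative response rate also accepts marrow CR: participants must "achieve a morphologic CR or marrow CR based on Investigator-assessed IWG criteria" and in addition be MRD-negative by central flow cytometry.
- **Population.** Entry is by MDS "with an IPSS-R risk category of intermediate, high, or very high risk", with no minimum blast percentage. The lower blast stratum is simply below 10%, and the progression row of Table 19 has a category headed "Less than 5% blasts".
- **Repeat marrows.** Protocol Table 3, footnote f: "Samples will be collected at Day 1 of Cycles 3, 5, and 7 and then every 3 cycles thereafter during study treatment". SAP 3.8.2 also includes unscheduled response assessments.
- **Testing.** ORR is first in the hierarchy of eight key secondary endpoints, which opens only after OS is significant (Protocol 8.3.1 and 8.5.2; SAP 2.1).

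**The concern.** For anyone at or below 5% blasts at baseline, the first half of the rule holds before treatment starts. What remains is a halving of a very small count, and one reading is enough.

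The other routes to response are better protected:

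- CR needs same-day recovery of blood counts (Protocol 5.3).
- PR needs a fall of at least half to a value still above 5%, so it cannot occur unless baseline exceeds 10%.
- HI must last at least 8 weeks from an abnormal pretreatment value, averaged over at least two measurements.

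Three things are at stake. Reported ORR may be too high in both arms. DOR may be timed from events that are not responses. The ORR difference may be diluted at the first gate of the hierarchy, where a failure stops the seven later tests. DOR is further affected because the relapse row in Table 19 covers only CR or PR, and blast progression from below 5% requires a rise above 5%. A drift back from 1% to 2% therefore does not end such a response.

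**Working it through.** **Plan's own figure.** The documents give no expected rate or power for ORR or marrow CR. As a check on the power formula, take the CR comparison in Protocol 8.1: 174 per arm, 20% vs 39%, two-sided 0.03.

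Power = Φ[(Δ − z·s0)/s1], with s0 = √(2p̄(1−p̄)/n) and s1 = √((p1(1−p1)+p2(1−p2))/n).

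This gives (0.19 − 2.170×0.0489)/0.0478 = 1.75, or 96%, against the stated 95%.

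**Step 1: chance of a false marrow CR.** Inputs from the documents: the criterion, and three scheduled marrows (Cycles 3, 5 and 7) within the 8 months that define ORR information. Assumed: n = 200, 500 or 1000 cells per marrow; the same true blast percentage p at every marrow; a non-zero baseline reading of at most 5%. A 0% baseline makes the relative fall undefined and is excluded.

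With baseline count x, one marrow qualifies with probability q(x) = P(Bin(n,p) ≤ x/2). Over k marrows the chance is 1 − (1−q)^k, averaged over x ~ Bin(n,p) restricted to 0 < x/n ≤ 5%.

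Example at p = 2%:
- 500 cells, baseline count 10: q = P(count ≤ 5) = 0.065; three marrows 1 − 0.935³ = 18%.
- 200 cells, baseline count 4: q = P(count ≤ 2) = 0.235; three marrows 55%.

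Averaged over the baseline reading, three marrows:

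| True blasts | 200 cells | 500 cells | 1000 cells |
|---|---|---|---|
| 1% | 68% | 41% | 21% |
| 2% | 47% | 21% | 6% |
| 3% | 33% | 10% | 2% |
| 4% | 19% | 3% | 0.2% |
| 5% | 8% | 0.4% | <0.1% |
| Uniform on 1-5% | 34% | 13% | 4% |

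Over five marrows (through Cycle 13) the uniform averages are 45%, 19% and 6%. Adding an assumed 30% coefficient of variation between aspirates raises the three-marrow figure at true 4% to 27% (200 cells) and 14% (500 cells).

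**Step 2: effect on ORR.** With share s of participants at or below 5% and false rate f among those not truly responding, ORR becomes p + (1−p)·s·f, and the difference shrinks by the factor (1 − s·f). Both s and f are assumed.

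- s = 10%, f = 17%: 45% becomes 45.9%.
- s = 20%, f = 30%: 45% becomes 48.3%.
- s = 35%, f = 45%: 45% becomes 53.7%; a 15-point gap becomes 15 × (1 − 0.1575) = 12.6 points.

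**Step 3: effect on power.** 260 per arm, unstratified, full information, same formula. Ranges run from the heaviest to the lightest of the three settings in Step 2.

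| True ORR | Two-sided α | Undiluted | Diluted |
|---|---|---|---|
| 45% vs 60% | 0.02 | 87% | 73-85% |
| 45% vs 60% | 0.05 | 93% | 84-92% |
| 45% vs 64% | 0.02 | 98% | 93-98% |
| 45% vs 70% or more | 0.02 | >99% | >99% |

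The 64% row borrows the 19-point gap planned for CR. Protocol 2.1.6 cites an ORR of 40-50% for azacitidine and 92% for the combination in the earlier study.

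**Step 4: what a >5% restriction leaves.** At a baseline reading of 5% or below the false rate becomes zero. With a reading above 5%, noise alone over three marrows still gives 21%, 7% and 1.6% at true 6%, 8% and 10% with 200 cells, and 1.8%, 0.3% and <0.1% with 500 cells.

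**The case against.** The strongest reply is that the consequence is small. The power loss is visible only if the true ORR difference is modest, and the Protocol's own background figures point to a large one. The smaller α of 0.02 applies only if CR was not rejected. ORR is tested only in a trial that has already shown a survival benefit. The noise rate depends on a cell count the documents do not give, and at true 4-5% with 500 cells it is about 3% or less. The calculation also applies the rule mechanically, and an investigator might not call 2% to 1% a marrow CR. All of this stands, and it limits the point to an overstated ORR, a mistimed DOR and a conditional power cost. It does not remove the gap in the definition.

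A reader might infer more than the documents support:

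- **Bias toward the arm that stays longer on treatment.** Not supported. Off treatment, marrows continue about every 8 weeks until new anticancer therapy or AML (Protocol Table 5 and 5.3). On treatment after Cycle 7 they come every 3 cycles, which is 12 weeks. Stopping treatment does not by itself reduce the chances to qualify.
- **Inflated type I error.** Not supported. Noise acting alike in both blinded arms raises both rates and narrows the difference.
- **A distorted MRD-negative rate.** Largely not. That endpoint also needs central MRD negativity with a 0.02% detection limit (Protocol 5.6.2), which a chance fall from 2% to 1% does not supply.
- **Damage to the primary endpoints.** None. CR requires count recovery, and OS does not use marrow data.

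**Conclusion.** The concern holds as a gap in the definition of ORR. As written, a participant who starts at or below 5% blasts can become an objective responder on a single halved reading. Noise alone would produce this over three marrows in about 34%, 13% or 4% of such participants (200, 500 or 1000 cells, true blasts uniform on 1-5%). The rate is much higher near 1% and close to nil at 4-5% with 500 cells or more. The cell count, the blast distribution, the share of participants at or below 5%, and literal application of the rule are all assumptions.

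ORR is overstated in both arms and some DOR clocks start at non-responses. The power cost is noticeable for a difference such as 45% vs 60%, small for 45% vs 64%, and negligible from 45% vs 70% upward, and it counts only after OS is significant. This is worth correcting, but it does not threaten the trial's main conclusions.

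**What to change.** Before unblinding, state in SAP 6.2.1, Protocol Table 19 and SAP Appendix Table 6 that marrow CR counts toward ORR, and starts DOR, only when baseline marrow blasts exceed 5%. Keep all randomized participants in the denominator; those at or below 5% can still respond by CR or HI. Report ORR under the current wording as a sensitivity analysis.

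If the sponsor prefers not to redefine a key secondary endpoint after the first interim analysis, keep the current definition and prespecify the restricted version as the sensitivity analysis.

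The cost is one sentence in each place, an entry in SAP Section 10 (which now reports no deviations from the protocol), and one programming condition on a baseline value already collected. SAP Section 1 says the plan is finalized before data finalization for the second interim, so there is a natural point to do it. The downsides are a slightly lower ORR in both arms, less comparability with historical ORR figures, and some remaining noise just above 5% if few cells are counted.
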